11. PHARMACOVIGILANCE

The Investigator is responsible for the detection and documentation of events meeting the criteria and definitions detailed below.

Full details of contraindications and side effects that have been reported following administration of the IMP can be found in the relevant Summary of Product Characteristics (SPC).

Participants will be instructed to contact their Investigator at any time after consenting to join the trial if any symptoms develop. All adverse events (AE) that occur after informed consent until EDD + 28 days must be recorded in the Case Report Form (CRF) or AE log. In the case of an AE, the Investigator should initiate the appropriate treatment according to their medical judgment.

11.1 DEFINITIONS

An **adverse event** (AE) is any untoward medical occurrence in a clinical trial participant which does not necessarily have a causal relationship with an investigational medicinal product (IMP).

An **adverse reaction** (AR) is any untoward and unintended response to an IMP which is related to any dose administered to that participant.

A serious adverse event (SAE), serious adverse reaction (SAR). Any AE or AR that at any dose:

- results in death of the clinical trial participant;
- is life threatening*;
- requires in-patient hospitalisation^ or prolongation of existing hospitalisation;
- results in persistent or significant disability or incapacity;
- consists of a congenital anomaly or birth defect;
- results in any other significant medical event not meeting the criteria above.

*Life-threatening in the definition of an SAE or SAR refers to an event where the participant was at risk of death at the time of the event. It does not refer to an event which hypothetically might have caused death if it were more severe.

CR007-T01 v4.0 PIPIN Protocol Version 5.0 17/05/2019 Page **30** of **45**

^Any hospitalisation that was planned prior to enrolment will not meet SAE criteria. Any hospitalisation that is planned post enrolment will meet the SAE criteria.

A suspected unexpected serious adverse reaction (SUSAR) is any AR that is classified as serious and is suspected to be related to the IMP, that it is not consistent with the information about the IMP in the Summary of Product Characteristics (SPC) or Investigators Brochure.

11.2 IDENTIFYING AES AND SAES

Participants will be asked about the occurrence of AEs and SAEs at every visit during the study. Open-ended and non-leading verbal questioning of the participant will be used to enquire about AE/SAE occurrence. Participants will also be asked if they have been admitted to hospital, had any accidents, used any new medicines or changed concomitant medication regimens. If there is any doubt as to whether a clinical observation is an AE, the event will be recorded.

AEs and SAEs may also be identified via information from support departments e.g. laboratories.

11.3 RECORDING AEs AND SAEs

When an AE/SAE occurs, it is the responsibility of the Investigator, or another suitably qualified physician in the research team who is delegated to record and report AEs/SAEs, to review all documentation (e.g. hospital notes, laboratory and diagnostic reports) related to the event. The Investigator will then record all relevant information in the CRF/AE log and on the SAE form (if the AE meets the criteria of serious).

Information to be collected includes dose, type of event, onset date, Investigator assessment of severity and causality, date of resolution as well as treatment required, investigations needed and outcome.

11.3.1 Pre-existing Medical Conditions

Pre-existing medical conditions (i.e. existed prior to informed consent) should be recorded as medical history and only recorded as adverse events if medically judged to have worsened during the study.

11.3.2 Worsening of the Underlying Condition during the Trial

Medical occurrences or symptoms of deterioration that are expected due to the participant's underlying condition should be recorded in the Participant's medical notes and only be recorded as AEs on the AE log if medically judged to have unexpectedly worsened during the study. Events that are consistent with the expected progression of the underlying disease should not be recorded as AEs.

11.4 ASSESSMENT OF AEs AND SAEs

Each AE must be assessed for seriousness, causality, severity and ARs must be assessed for expectedness by the Principal Investigator or another suitably qualified physician in the research team who has been delegated this role.

For randomised double blind studies, AEs will be assessed as though the participant is taking active IMP. SUSARs will be unblinded by ACCORD before they are reported to REC and CA (by ACCORD).

The Chief Investigator (CI) may not downgrade an event that has been assessed by an Investigator as an SAE or SUSAR, but can upgrade an AE to an SAE, SAR or SUSAR if appropriate.

11.4.1 Assessment of Seriousness

The Investigator will make an assessment of seriousness as defined in Section 10.1.

11.4.2 Assessment of Causality

CR007-T01 v4.0 PIPIN Protocol Version 5.0 17/05/2019 Page **31** of **45** The Investigator will make an assessment of whether the AE/SAE is likely to be related to the IMP according to the definitions below.

• Unrelated: where an event is not considered to be related to the IMP.

• Possibly Related: The nature of the event, the underlying medical condition, concomitant medication or temporal relationship make it possible that the AE has a causal relationship to the study drug. The assessment of causality will be made against the reference safety information found in the reference safety information of the SPC (refer to the appropriate section).

Where non Investigational Medicinal Products (NIMPs) e.g. rescue/escape drugs are given: if the AE is considered to be related to an interaction between the IMP and the NIMP, or where the AE might be linked to either the IMP or the NIMP but cannot be clearly attributed to either one of these, the event will be considered as an AR. Alternative causes such as natural history of the underlying disease, other risk factors and the temporal relationship of the event to the treatment should be considered and investigated. The blind should not be broken for the purpose of making this assessment.

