Compliance (number of tablets taken) will be collected from the participants' medical records and at the day 7 trial visit (from the participant's diary) and the returned medication bottles. Serum pravastatin levels will also be taken to evaluate compliance.

Timing from presentation to first dose administered

Timing of presentation to first treatment dose administered will be collected from the participants' medical records.

Delivery, post-natal and neonatal outcomes

At the time of delivery, secondary outcomes of gestational age at delivery, markers of fetal and maternal inflammation and pravastatin levels will be collected (via medical records and maternal and cord blood samples).

Maternal and neonatal outcomes will be monitored and information extracted from the participants medical records until EDD + 28 days.

Acceptability of the Trial

This will be collected at two points:

- 1) Percentage uptake of eligible participants to the trial
- 2) At or near 28 days post EDD, participants will be contacted using their preferred method of contact, thanked for their involvement and asked for feedback.

Stopping Rules

We have set the following safety rules for PIPIN based on maternal and neonatal deaths that are possibly or definitely related to IMP. We have based these rules on the expected frequency of maternal and neonatal deaths in the population.

CR007-T01 v4.0 PIPIN Protocol Version 5.0 17/05/2019 Page **16** of **45**

We do not anticipate that there will be any maternal deaths (maternal death rate in the UK is 8.5 per 100,000). So in n=40 women we would not expect any deaths – we would need to recruit almost 12,000 women to expect 1 death.

We anticipate that the death rate of babies in the PIPIN population will be at least 6% (based on the Oracle study, which also recruited women in preterm labour (Kenyon et al. 2001). The Oracle study recruited women suspected clinically to be in preterm labour; in PIPIN we will recruit women in whom a "test" has additionally confirmed the onset of preterm labour, hence preterm birth (with associated neonatal death) is more likely to occur in PIPIN).

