With an expected death rate of 6%, we consider that a doubling of this rate would be grounds for serious concern, if such deaths were thought to be related or possibly related to study IMP, that will prompt a halt in recruitment pending review by the independent DMC (iDMC), We will randomize around 20 to pravastatin, and assume there is no cross over from placebo to pravastatin (although of course as safety data these will be analysed according to treatment received). If there is 1 death thought to be related to IMP in any the first 10 randomised to pravastatin, or cumulatively 2 deaths in the first 20 randomised to pravastatin, this will trigger a review by the iDMC, and if the iDMC believes that it is plausible that the deaths are related to the IMP, the DMC will advise whether the trial should be stopped, or the circumstances under which the trial should continue.

The two most severe class side effects of statins, that is liver toxicity (defined by jaundice, hepatitis or fulminant hepatic necrosis) and muscular toxicity (rhabdomyolysis), both occur at a frequency of less than 1 < 10,000. Occurrence of these in any participant with reasonable suspicion of causation due to the IMP will prompt review of unblinded data by the DMC.

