11.4.3 Assessment of Expectedness

If the event is an AE the evaluation of expectedness will be made based on knowledge of the reaction and the relevant product information documented in the SPC.

The event may be classed as either:

Expected: the AE is consistent with the toxicity of the IMP listed in the SPC.

Unexpected: the AE is not consistent with the toxicity in the SPC.

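### Section 11.4.2 ties causality to the SPC safety information that serves to decide expectedness, which conflicts with its own clinical definition of 'Possibly Related' and works against the SUSAR definition

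*Protocol*

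**What the plan says.** Section 11.4.2 of the protocol gives two causality categories, Unrelated and Possibly Related. The second is defined on clinical grounds: "The nature of the event, the underlying medical condition, concomitant medication or temporal relationship make it possible that the AE has a causal relationship". Directly after this, the same bullet adds: "The assessment of causality will be made against the reference safety information found in the reference safety information of the SPC". Later in the section the investigator is asked to look into other explanations, in a sentence that opens: "Alternative causes such as natural history of the underlying disease, other risk factors and the temporal relationship of the event to the treatment should be".

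Section 11.4.3 uses the SPC for a different question, whether the event was foreseen: "Unexpected: the AE is not consistent with the toxicity in the SPC".

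Section 11.1 defines a SUSAR as a serious reaction that is "suspected to be related to the IMP, that it is not consistent with the information about the IMP in the Summary of Product Characteristics" or the Investigators Brochure. Section 11.6 sets the 7-day and 15-day reporting times for SUSARs and describes the annual safety report as a list of SARs and SUSARs.

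The safety rules in section 3 (Stopping Rules) are "based on maternal and neonatal deaths that are possibly or definitely related to IMP". The DMC review is triggered by 1 related death among the first 10 women randomised to pravastatin, or 2 cumulatively among the first 20. A separate rule covers liver toxicity and rhabdomyolysis: a case "with reasonable suspicion of causation due to the IMP will prompt review of unblinded data by the DMC".

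**The concern.** Causality asks whether the drug may have caused the event. Expectedness asks whether the product information already describes it. A SUSAR exists only where the answers are 'perhaps' and 'no'. If the product information is the yardstick for both, the first answer is pulled towards 'unrelated' in exactly the cases where the second is 'unexpected'.

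The wording also leaves the investigator with two instructions in one bullet. One is clinical and has a low threshold. The other is phrased as mandatory and points to the SPC. The protocol does not say which governs an event that the SPC does not list.

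This matters more here than in a trial of a drug in its usual setting. Section 1.2 says that statins are used for hypercholesterolaemia and coronary heart disease and were until fairly recently contraindicated in pregnancy. The trial gives one to women in preterm labour, with fetal and neonatal safety among the endpoints in section 2.2.2. If the SPC lists few fetal or neonatal reactions, those are the events most exposed to under-classification. The SPC is not part of the documents, so that condition is an assumption.

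**Working it through.** No figure in the protocol rests on this sentence, so there is nothing to reproduce. The check is mainly a comparison of the text.

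**Step 1. The three definitions side by side, for a serious event with plausible timing that the SPC does not list**

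| Place | Question | Yardstick | Result |
|---|---|---|---|
| 11.4.2, definition | Possibly related? | Nature of event, underlying condition, other medication or timing | Yes |
| 11.4.2, next sentence | Possibly related? | SPC reference safety information | Unclear; literally, towards no |
| 11.4.3 | Expected? | SPC | No |
| 11.1 | SUSAR? | Serious, suspected related, not consistent with the SPC | Depends on which line of 11.4.2 is followed |

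The conflict is therefore inside 11.4.2, and it decides the SUSAR classification for this kind of event.

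**Step 2. What depends on the rating**

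- Expedited reporting under 11.6 applies to SUSARs. An event rated unrelated is neither a SAR nor a SUSAR, so it also falls outside the annual list as described there.
- The death rule in section 3 counts only deaths judged related or possibly related. Section 11.4.2 is the only place where the protocol says how relatedness is judged.
- The liver and muscle rule concerns events that section 3 itself calls class side effects of statins, and it has its own standard of reasonable suspicion. An appeal to known toxicity would not tend to push these towards unrelated.

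**Step 3. Illustration: how sensitive the death rule is to the relatedness rating**

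Inputs from section 3: an expected death rate of babies of 6%; a doubling as grounds for serious concern, 2 × 6% = 12%; the rule of 1 in the first 10 or 2 in 20 on pravastatin. Assumed, because the documents give no value: q, the share of deaths rated related. Deaths are taken as independent with the same rate throughout.

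With death rate d, the rate of related deaths is r = d × q. The rule is not met only if there are no related deaths in the first 10 and at most one in the next 10, so

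P(rule met) = 1 − (1 − r)^10 × [(1 − r)^10 + 10 r (1 − r)^9].

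For d = 0.12 and q = 1, r = 0.12: 0.88^10 = 0.2785 and 10 × 0.12 × 0.88^9 = 0.3798, so P = 1 − 0.2785 × 0.6583 = 0.817.

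For d = 0.12 and q = 0.5, r = 0.06: 0.94^10 = 0.5386 and 10 × 0.06 × 0.94^9 = 0.3438, so P = 1 − 0.5386 × 0.8824 = 0.525.

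| q (assumed) | P at d = 12% | P at d = 6% |
|---|---|---|
| 1 | 0.817 | 0.525 |
| 0.5 | 0.525 | 0.288 |
| 0.25 | 0.288 | 0.148 |
| 0.1 | 0.119 | 0.060 |

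The table shows that the rule depends strongly on the relatedness rating. It does not measure the effect of the sentence: some deaths after preterm birth would rightly be rated unrelated, and nothing in the documents says how far the sentence would move q.

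**The case against.** A reader might infer that, with one yardstick for both judgements, an unlisted event cannot become a SUSAR at all. The documents do not support that. Being assessed against the SPC is not the same as having to be listed in it, and known toxicity is a normal input to a causality judgement. Unrelated is defined simply as not considered related, and no text makes an unlisted event unrelated. The definition of Possibly Related joins its criteria with 'or' and needs only that they make a causal link possible. The protocol also plainly expects that SUSARs can occur: it provides for unblinding them (5.5.3, 11.4), for withdrawal because of them (5.6) and for reporting them (11.6).

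There are safeguards as well. Under 11.4 events are assessed as though the participant were on active drug, and the Chief Investigator may upgrade an event to a SUSAR but may not downgrade one. Under 11.5 SAEs go to the sponsor's office within 24 hours whatever their causality, apart from the listed exclusions.

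A reader might also infer that every DMC trigger is weakened. That fails for the liver and muscle rule, for the reason in step 2. The death rule has its own wording too, and cites neither 11.4.2 nor the SPC.

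Finally, the sentence repeats itself and looks like a drafting slip.

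Most of this stands, and it limits the consequences. It does not remove the conflict. The safeguards are partial: the first SAE report already carries the investigator's causality rating, and no other causality standard is given to guide an upgrade. A slip in an operative safety definition can still be followed as written.

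**Conclusion.** The point holds in a limited form. Section 11.4.2 applies the expectedness benchmark to causality, contradicts the clinical definition in its own bullet and works against the SUSAR definition in 11.1. Followed literally, it could cause serious events that the SPC does not list to be rated unrelated. The parts of the plan plausibly exposed are SUSAR classification with its expedited reporting, and the death rule.

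Its size cannot be fixed from the documents. That would require knowing what the SPC lists and how raters would weigh the sentence, and neither is given. The probabilities for the death rule rest on an assumed q and independent deaths, and show sensitivity only. The documents give no ground for a q near 0, because the definition of Possibly Related does not depend on SPC listing. This is a worthwhile correction to safety wording, not a failure of the safety system.

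**What to change.** Delete the sentence from 11.4.2 or move it to 11.4.3. State in 11.4.2 that causality is judged on the clinical criteria already listed there (nature of the event, underlying condition, other medication, timing, alternative causes) whether or not the event appears in the SPC. State in 11.4.3 that the reference safety information is used only for expectedness. Bring any guidance on the SAE form into line.

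The cost is a small wording amendment. The downside is that a few more events may be rated possibly related, with some additional reporting work.

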11.4.3 Assessment of Expectedness

If the event is an AE the evaluation of expectedness will be made based on knowledge of the reaction and the relevant product information documented in the SPC.

The event may be classed as either:

Expected: the AE is consistent with the toxicity of the IMP listed in the SPC.

Unexpected: the AE is not consistent with the toxicity in the SPC.

11.4.4 Assessment of Severity

The Investigator will make an assessment of severity for each AE/SAE/SAR/SUSAR and record this on the CRF/AE log or SAE form according to one of the following categories:

Mild: an event that is easily tolerated by the participant, causing minimal discomfort and not interfering with every day activities.

Moderate: an event that is sufficiently discomforting to interfere with normal everyday activities.

Severe: an event that prevents normal everyday activities.

Note: the term 'severe', used to describe the intensity, should not be confused with 'serious' which is a regulatory definition based on participant/event outcome or action criteria. For example, a headache may be severe but not serious, while a minor stroke is serious but may not be severe.

11.5 REPORTING OF SAEs/SARs/SUSARs

Once the Investigator becomes aware that an SAE has occurred in a study participant, the information will be reported to the ACCORD Research Governance **within 24 hours**. If the Investigator does not have all information regarding an SAE, they should not wait for this additional information before notifying ACCORD. The SAE report form can be updated when the additional information is received.

The SAE report will provide an assessment of causality and expectedness at the time of the initial report to ACCORD according to Sections 10.4.2, Assessment of Causality and 10.4.3, Assessment of Expectedness.

The SAE form will be transmitted via email to [contact] Only forms in a pdf format will be accepted by ACCORD via email. Forms may also be sent by fax to ACCORD on **[name] or may be submitted by hand to the office. Where missing information has not been sent to ACCORD after an initial report, ACCORD will contact the Investigator and request the missing information. The Investigator must respond to these requests in a timely manner.

CR007-T01 v4.0 PIPIN Protocol Version 5.0 17/05/2019 Page **32** of **45** All reports faxed to ACCORD and any follow up information will be retained by the Investigator in the Investigator Site File (ISF).

For this study the following events are **NOT** considered SAEs:

- Pregnancy is not considered an AE or SAE, as it is part of the inclusion criteria
- Hospitalisations for treatment planned prior to randomisation and hospitalisation for elective treatment of a pre-existing condition will not be considered as an SAE. This includes pregnancy. However, *complications occurring during such hospitalisation will be AE/SAEs.*
- The following are also not considered SAEs
 - Preterm delivery
 - Hospitalisation for "maternal discomfort"
 - Hospitalisation for "observation" or "monitoring" for which the women is admitted for a period of less than 12 hours
 - Delivery complications such as caesarean section or post-partum haemorrhage
 - Admission of the baby to the neonatal unit for a period of up to 14 days.

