1. INTRODUCTION

1.1 BACKGROUND

Spontaneous preterm labour is the biggest cause of preterm birth (Norman et al. 2009). Preterm birth is itself the major cause of infant mortality and morbidity, accounting for 11% of births worldwide (Blencowe et al. 2012). It is estimated that nearly one million children every year have neurodevelopmental disability as a direct consequence of preterm birth (Blencowe et al. 2013), with pulmonary, cardiac and gastrointestinal dysfunction all described in surviving infants (Rubens et al. 2014)

The aetiology of preterm birth remains an incompletely understood process, with roughly 75% occurring spontaneously in the UK (the remainder being iatrogenic for maternal or fetal reasons) (Rubens et al. 2014). Known aetiological factors contributing to preterm birth include infection and inflammation, uteroplacental haemorrhage or ischaemia, or uterine over distension such as in the multiple pregnancy(Goldenberg et al. 2008). There are also several well described clinical risk factors including previous preterm birth

Currently available treatments options include antibiotics, tocolysis and magnesium sulphate (for fetal neuroprotection as opposed to arrest of labour).(Preterm labour and birth | Guidance and guidelines | NICE n.d.) Unfortunately neither antibiotics nor tocolysis have been shown to provide short term benefit to both the mother and fetus (only in certain circumstances), and no long term benefit to children born at 37 weeks gestation or less (Flenady et al. 2013, Haas et al. 2012).

Magnesium sulphate, whilst recommended by NICE for fetal neuroprotection, does not prevent preterm labour. (Preterm labour and birth | Guidance and guidelines | NICE n.d.)

As considerable evidence implicates inflammatory mediators in both the underlying mechanisms of parturition (term and preterm), and initiation of brain damage which leads to neurodevelopmental disability associated with preterm delivery (Boyle et al. 2017), it follows that the ideal agent for the treatment of preterm labour would be one which both inhibits myometrial contractility and conveys anti-inflammatory benefit. Our *in vitro* and pre-clinical *in vivo* studies suggest that statins have both actions. We hypothesise that statins may reduce preterm labour associated preterm birth AND reduce long term neurodevelopmental disability.

CR007-T01 v4.0 PIPIN Protocol Version 5.0 17/05/2019 Page **11** of **45**

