2.2.2 Secondary Endpoints

Secondary Endpoints:

- 1) Retention, adherence and ability to collect clinical outcomes from participants
- 2) Time to delivery from presentation and gestation at delivery
- 3) Contraction frequency as monitored at presentation and from randomisation to delivery or cessation of regular uterine activity.
- 4) Maternal markers of inflammation including, but not limited to: IL-6, IL-10, IL-13, IL-17, TNFa, IL-1RA, sTNF-RI, sTNF-R2, and HO-1, as well as levels of the soluble IL-6R and the inhibitor spg130 (abbreviated hereafter to 'Inflammatory Profile')
- 5) Fetal measures of inflammation including but not limited to: (cord IL-1, IL-6, IL-8, sIL-6R and sgp130.
- 6) Adverse events (maternal and fetal)
- 7) Time from time first seen in an acute obstetric care setting to administration of trial medication as documented in the participant medical records.
- 8) Compliance with 7 days of blinded treatment
- 9) Acceptability of the trial to those who have participated
- 10) Pharmacokinetic parameters as compared with current published data
- 11) Maternal outcomes:
 - a. Proven maternal infection
 - b. Safety of intervention to mother (self-reported AEs and biochemical monitoring of liver function tests and creatinine kinase).
 - c. Pre-labour ROM
 - d. Duration, location and level of care of hospital stay following presentation with suspected preterm labour AND following delivery.
- 12) Neonatal outcomes:
 - a. Details of in utero transfers including mode of transport required
 - b. Gestational age at delivery, morbidity and mortality, birthweight, duration and location of hospital stay post-delivery and up to 28 days post EDD.
 - c. Safety of intervention

CR007-T01 v4.0 PIPIN Protocol Version 5.0 17/05/2019 Page **14** of **45**

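### The SAE exemption for delivery complications has no severity or causality limit, so a life-threatening or possibly drug-related post-partum haemorrhage could be classed as non-serious, and haemorrhage is not a named maternal outcome

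*Protocol*

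**What the plan says.** Protocol section 11.5 requires SAEs to reach the sponsor's office within 24 hours and then lists exceptions. Under the lead-in "The following are also not considered SAEs" stands the item "Delivery complications such as caesarean section or post-partum haemorrhage". Two other items in that list carry a numerical limit: under 12 hours for observation or monitoring, and up to 14 days for neonatal unit admission. This item has none. An earlier bullet in the same section covers planned and elective hospitalisation, says that this includes pregnancy, and adds that "complications occurring during such hospitalisation will be AE/SAEs".

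Section 11.1 counts an AE as serious if, among other criteria, it "is life threatening". The same section defines a SUSAR as a reaction classified as serious. Section 11.6 says that the annual safety report lists SARs and SUSARs.

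Section 1.1 describes the ideal agent as "one which both inhibits myometrial contractility and conveys anti-inflammatory benefit" and says that the team's laboratory and animal studies suggest statins do both. Treatment runs for 7 days or to delivery, whichever is sooner (sections 3 and 5.5.2).

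The maternal outcomes in section 2.2.2 item 11, repeated in section 10.2 item 11a, are proven infection, self-reported AEs with liver function tests and CK, pre-labour rupture of membranes, and "Duration, location and level of care of hospital stay following presentation with suspected preterm labour AND following delivery". Haemorrhage, blood loss and mode of delivery are not listed.

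**The concern.** The exemption removes serious status by type of event, whereas the general definition assigns it by consequence. For a life-threatening haemorrhage the two give opposite answers, and an investigator has to choose between them within 24 hours.

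Classification decides what follows. An event that is not serious cannot be a SAR or SUSAR under section 11.1, so it reaches neither expedited reporting nor the annual list. The exempted event is also one that the rationale makes worth watching. A drug intended to reduce uterine contractility, given up to delivery, could plausibly affect contraction of the uterus after birth. The first secondary objective (section 2.1.2) asks about longer time to delivery and fewer contractions without adverse effects, so the grading of this harm bears on a stated aim.

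**Working it through.** The core of the check is textual.

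**1. Scope of the exemption.** The lead-in to the list removes SAE status only. By contrast, another bullet in section 11.5 says "Pregnancy is not considered an AE or SAE, as it is part of the inclusion criteria". Pregnancy is taken out of both categories; delivery complications are taken out of one. A haemorrhage therefore remains an AE.

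**2. Conflict.** Section 11.1: life-threatening means serious. Section 11.5: post-partum haemorrhage is not serious, whatever its severity. Both cannot hold for a life-threatening haemorrhage. The sentence on complications during hospitalisation is in tension with the exemption but does not flatly contradict it, since the later list can be read as naming exceptions to it.

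**3. Reporting consequence.** Not an SAE, so not a SAR or SUSAR (11.1), so outside the 24-hour rule (11.5), the 7- and 15-day SUSAR rules and the annual list (11.6). The review triggers under Stopping Rules in section 3 are IMP-related deaths and liver or muscle toxicity, so a non-fatal haemorrhage meets none of them.

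**4. Routes that remain open.**
- All AEs from consent to EDD + 28 days must be recorded (section 11, opening text), and health records are monitored over that period (7.4).
- Each AE is assessed for seriousness, causality and severity as though the woman were on active drug, and the Chief Investigator may upgrade an AE (11.4).
- AEs are secondary endpoint 6 (2.2.2) and are compared between arms (10.2 item 9 and closing paragraph).
- Maternal mortality and morbidity is scheduled at delivery and at 28 days post EDD (table in 7.2). The glossary in Appendix 4 defines neonatal morbidity but not maternal morbidity.

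**5. Scale.** The Protocol gives no haemorrhage rate. The following rests on assumed rates; only the figure of about 20 women randomised to pravastatin (section 3) comes from the document.
- Events of any severity among 20 women: 20 × 0.05 = 1; 20 × 0.15 = 3.
- Chance of at least one: 1 − 0.95^20 = 0.64; 1 − 0.85^20 = 0.96.
- If half deliver within the dosing week (a further assumption), 10 women: 10 × 0.05 = 0.5; 10 × 0.15 = 1.5. Chance of at least one: 1 − 0.95^10 = 0.40; 1 − 0.85^10 = 0.80.
- No events in 20 would still leave a one-sided 95% upper limit of 1 − 0.05^(1/20) = 13.9%.
- Approximate power to detect a doubling with 20 per arm, two-sided 5%, is about 6% at an assumed control rate of 2% and 28% at 20%. For the latter, 0.20 against 0.40: null standard error √(2 × 0.3 × 0.7/20) = 0.145, alternative standard error √((0.16 + 0.24)/20) = 0.141, power Φ((0.20 − 1.96 × 0.145)/0.141), about 0.28.

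A comparison by arm can therefore only be descriptive. With so few events, the seriousness and causality judgement on each case carries most of the safety information.

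**The case against.** The strongest reply is that section 11.5 is a deliberate, trial-specific exception to a general definition. Caesarean section and haemorrhage are ordinary events at delivery, and reporting each as an SAE would swamp a 40-woman feasibility study. That is a fair reason for an exemption. It does not explain why this one reaches life-threatening or suspected-related events.

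A second reply is that the mechanism is speculative. The contractility evidence described in section 1.2 is for 50µM simvastatin on induced contractions in a myometrial cell line. It concerns neither pravastatin nor uterine tone after birth, and the same section reports no major safety issues in an earlier pravastatin trial. This stands as a limit: haemorrhage is a foreseeable harm by inference, not a documented one. The conflict between 11.1 and 11.5 does not depend on it.

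A reader might go further and infer that haemorrhage cannot reach the safety conclusion, would get no SUSAR assessment, or would have no line in the results. The documents do not support this, because the routes in step 4 of the working are open. Nor does section 11.3.2 clearly keep haemorrhage off the AE log: it concerns expected progression of the underlying condition, and section 11.2 says that doubtful observations are recorded. A reader might also apply an assumed rate to all 40 women. Only about 20 receive pravastatin, fewer deliver on drug, and the assumed rate covers haemorrhage of any severity.

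Finally, what the DMC receives may be set out in its charter (section 12.3), and table layout belongs to the analysis plan. Neither document is shown, so no gap is claimed there.

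**Conclusion.** The point holds as a fault in classification and in named outcomes. The exemption in section 11.5 has no severity or causality limit and conflicts with section 11.1. Followed literally, a life-threatening or possibly drug-related haemorrhage is a non-serious AE unless upgraded at discretion, and it could miss 24-hour, SUSAR and annual SAR reporting. Haemorrhage, blood loss and mode of delivery are not named maternal outcomes, so their appearance by arm depends on AE logging and on a maternal morbidity row with no definition. The events are under-classified, not hidden.

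The size is modest and rests on assumption: 1 to 3 haemorrhages of any severity among about 20 women on pravastatin at 5% to 15%, fewer among those delivering on drug, and fewer still life-threatening. No powered comparison is implied.

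**What to change.** 1. In section 11.5, state that the exemption does not cover delivery complications that are fatal, life-threatening or suspected to be related to the IMP. Reconcile the item with the seriousness criteria in 11.1 and with the sentence on complications during hospitalisation.
2. State that exempted delivery complications are still recorded as AEs, so that section 11.3.2 cannot be read to exclude them.
3. In section 2.2.2 item 11 and section 10.2 item 11a, add post-partum haemorrhage or recorded blood loss, against a stated definition, and mode of delivery. Take them from the maternity record and report them descriptively by arm, split by delivery within or after the dosing period.

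Cost: protocol wording, a few more SAE forms, and two or three CRF fields filled from records already reviewed to EDD + 28 days. Sample size and primary endpoint are unaffected.
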